**Faraday Study**

**Study Protocol**

Patients aged 18 years and older with HBsAg positivity for more than six months and HBV-DNA level  $>2,000$  IU/ml were included in the study. Written informed consent was obtained from all participants. The exclusion criteria were established as presence of cirrhosis, alcohol consumption  $>140$  g/week for women and 210 g/week for men, hepatitis C, hepatitis D and/or HIV coinfections.

The baseline characteristics including patient demographics, BMI, comorbidities, LSM and CAP via transient elastography (FibroScan®), liver ultrasound, HBV serology, platelet count, ALT, HBV viral load.

All patients underwent liver biopsy before initiating antiviral therapy, with a maximum interval of two week between liver biopsy and the FibroScan®.

Transient elastography was performed by a certified operator, using the M probe for patients with skin to capsule distance  $< 2.5$  cm or an XL probe for patients with skin to capsule distance  $> 2.5$  cm. Patients were fasted for  $> 2$  h before FibroScan®. At least 10 successful measurements were performed and recorded.

Fibrosis stage by Liver Stiffness Measurement (LSM) and steatosis by Controlled Attenuation Parameter (CAP) were investigated on FibroScan® for MASLD and MASH. Obese or diabetic patients with a CAP value  $>240$  dB/m were considered MASLD. Patients with normal BMI and nondiabetic patients had at least two risk factors for metabolic dysfunction were also considered to have MASLD. Patients with MASLD and concomitant necroinflammation in the liver were

considered as MASH. Necroinflammation was considered as LSM  $\geq 7.2$  kPa in patients with MASLD or LSM  $> 5.5$  kPa in patients with liver injury (histologic and/or ALT>NSU).

The study protocol was approved by the Ethics Committee of Dicle University (Protocol number: 2022/261).

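### The second MASLD branch states no steatosis condition, so the rule as written can label a patient at or below the CAP cut-off as MASLD, and as MASH

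*Combined protocol and SAP*

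**What the plan says.** All the relevant text is in the Study Protocol section of the combined protocol and SAP.

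- **Lead-in:** the section says that "steatosis by Controlled Attenuation Parameter (CAP) were investigated on FibroScan® for MASLD and MASH". It gives no threshold here and does not say that steatosis is required in every route.
- **First route to MASLD:** "Obese or diabetic patients with a CAP value" above 240 dB/m.
- **Second route to MASLD:** "Patients with normal BMI and nondiabetic patients had at least two risk factors for metabolic dysfunction were also considered to have MASLD".
- **MASH:** "Patients with MASLD and concomitant necroinflammation in the liver were" classed as MASH. Necroinflammation means LSM ≥7.2 kPa in MASLD, or LSM >5.5 "kPa in patients with liver injury (histologic and/or ALT>NSU"). Neither limb mentions CAP.
- **Data available:** CAP is a listed baseline variable ("The baseline characteristics including patient demographics, BMI, comorbidities, LSM and CAP via transient elastography"). Ultrasound is on the same list ("liver ultrasound, HBV serology, platelet count, ALT, HBV viral load"), and "All patients underwent liver biopsy before initiating antiviral therapy".

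The Statistical Analysis section says that categorical variables are shown as numbers and percentages and that Spearman correlations were run. It does not name the variables and adds nothing to the MASLD definition.

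**The concern.** The protocol uses CAP to establish steatosis, but the only cut-off sits inside the first route. The second route rests on metabolic risk factors alone. A patient with no evidence of steatosis can therefore receive a label that the protocol elsewhere ties to steatosis. MASH is defined within MASLD, so the gap reaches both labels.

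If the literal rule was the one coded, the MASLD and MASH counts and percentages would include patients at or below the CAP cut-off, and any analysis using those labels would inherit them. Correlations among directly recorded values (LSM, CAP, ALT, viral load) do not use the labels and are unaffected.

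**Working it through.** The documents give no sample size and no MASLD or MASH count, so there is no stated figure to reproduce. The check applies the rule to example patients.

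**Step 1: could another sentence supply the condition?** The entry criteria cover age, HBsAg, HBV-DNA, cirrhosis, alcohol and coinfections. None concerns steatosis. The MASH rule uses LSM, with or without liver injury. The Statistical Analysis section is silent. So nothing supplies it.

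**Step 2: apply the rule.** Each patient below has normal BMI, no diabetes, two metabolic risk factors and CAP 180 dB/m. *Literal* means no CAP condition in the second route; *carried over* means CAP >240 dB/m is required there too.

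| Patient | LSM (kPa) | Liver injury | Literal | Carried over |
|---|---|---|---|---|
| A | 7.5 | not needed | MASLD and MASH | neither |
| A2 | 6.0 | yes | MASLD and MASH | neither |
| A3 | 6.0 | no | MASLD only | neither |

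**Step 3: confirm by enumeration.** Take 3 BMI classes × 2 diabetes states × 2 risk-factor states × 4 CAP values (200, 240, 241, 300) × 3 LSM values (5.0, 6.0, 7.2) × 2 injury states = 288 profiles. Read the second route as normal BMI *and* non-diabetic. The literal rule then labels 1 × 2 × 3 × 2 = 12 profiles with CAP ≤240 dB/m as MASLD. Of the 6 LSM-by-injury combinations, 3 meet the necroinflammation rule, so 2 × 3 = 6 of the 12 are MASH. All 12 enter by the second route. With CAP >240 dB/m required in both routes, the counts are 0 and 0. These are grid cells that show the path exists, not patient frequencies.

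**Step 4: size.** Let N be the patients analysed and x the second-route patients with CAP ≤240 dB/m. If no steatosis test of any kind was applied to that route, the MASLD percentage, judged against the CAP cut-off, is too high by 100·x/N points. The MASH excess is at most the same, since only those of the x who meet the LSM rule count. If CAP, ultrasound or biopsy steatosis was required, the excess is zero, even if some of these patients had CAP ≤240 dB/m but steatosis on another test. Neither x nor N is given.

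**Step 5: a separate wording point.** The same sentence does not settle whether normal BMI and no diabetes must both hold, or either. Each patient below has two risk factors and LSM 7.5 kPa.

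| Patient | If both | If either |
|---|---|---|
| Obese, non-diabetic, CAP 180 | neither label | MASLD and MASH if literal; neither if carried over |
| Overweight but not obese, non-diabetic, CAP 300 | neither label | MASLD and MASH |

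The second patient does not depend on the CAP gap at all.

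**The case against.** The best defence is that this is a drafting slip. The lead-in ties CAP to MASLD and MASH without limiting it to a subgroup. The second-route sentence uses *also*, and its grammar is visibly broken. Read as one paragraph, CAP could be common to both routes, which would then differ only in their metabolic entry condition. That is plausible, and it stands as a reason not to assume a classification fault. It does not remove the gap: the lead-in says that steatosis was investigated, not that it was required, and *also* can equally mean in addition to those who qualify by CAP. Two coders could apply different rules and both point to this paragraph.

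A second objection is that ultrasound and biopsy were available, so steatosis may have been established without CAP. This stands too, and it is why the 100·x/N expression is conditional. The text does not name either test for this purpose.

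Third, no endpoint or named test is tied to the labels. That is correct and limits the traceable effect to descriptive counts and to whatever analyses used the labels.

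A reader might infer that patients without steatosis were in fact counted as MASLD, or that the MASLD percentage is inflated. The documents do not support either inference. They do not say which rule was coded and give no counts.

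**Conclusion.** The point holds as a defect in the stated rule. CAP >240 dB/m is attached only to obese or diabetic patients, and no steatosis condition of any kind is stated for the second route. Followed exactly, the rule can give MASLD, and MASH, to a patient with CAP ≤240 dB/m and no steatosis. Confidence is high that the condition is missing from the text; it does not extend to any claim about how patients were coded.

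The size is unknown and may be zero; the expression in the working applies only if no steatosis test was used. Nor can one assume that tidying the whole sentence would lower the MASLD count. Settling the both-or-either wording could bring in overweight, non-diabetic patients who now fit neither route, so the net direction is unknown.

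**What to change.** 1. Amend the second-route sentence so that it also requires steatosis. Use the CAP >240 dB/m cut-off already stated for the first route, or name ultrasound or biopsy if that was the test used.
2. Check which rule was used in coding. If no steatosis test was applied, recode MASLD, then MASH, and re-run the counts and any analysis that uses these labels. If a test was applied, only the text needs correcting.
3. Report how many second-route candidates, counted before any CAP condition, had CAP ≤240 dB/m.

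As a secondary clarification, state whether normal BMI and no diabetes must both hold or either, and where overweight, non-obese, non-diabetic patients fall.

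The cost is a check of the coding, one or two clauses and one reported count. CAP is already collected, so no new data are needed. The downside is a possible change in the MASLD and MASH counts and, since the text is in the past tense and the analysis may be complete, a re-run of label-based results.

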### **Statistical Analysis**

The IBM SPSS 21.0 statistical software for Windows was used for the statistical evaluation of the research data. The measurable variables were presented as the mean  $\pm$  standard deviation (SD), while the categorical variables were presented as the number and percentage (%). Spearman's rho correlation analysis was performed to determine the relationship between the variables. The hypotheses were bidirectional, and  $p \leq 0.05$  was considered statistically significant.

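### Does a single mean ± SD rule for all continuous variables make the baseline summary of HBV-DNA misleading?

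*Combined protocol and SAP*

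**What the plan says.** The Statistical Analysis section has two descriptive rules. For continuous data, "The measurable variables were presented as the mean" ± SD; for the rest, "while the categorical variables were presented as the number and percentage". It offers no median and interquartile range, no normality check and no log scale. Its one method of inference is rank-based: "Spearman's rho correlation analysis was performed to determine the relationship between the variables".

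The Study Protocol section refers to HBV-DNA twice. As an entry criterion it has a unit and a floor: "HBV-DNA level $>2,000$ IU/ml were included in the study". As a baseline characteristic it has neither: "HBV serology, platelet count, ALT, HBV viral load". No upper limit, assay range, expected distribution or sample size is given.

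**The concern.** Viral load has a floor at 2,000 IU/ml and nothing above it, so values may run over several orders of magnitude. On the raw scale the highest values can then pull the mean well above the median and make the SD larger than the mean. A baseline table could show an interval of mean ± SD reaching below zero although every eligible patient exceeds 2,000 IU/ml. A reader could not recover the typical viral load or its spread from that entry.

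What is at stake is how well readers can see who was studied, since viral load helps define eligibility. ALT raises the same question more mildly. It also looks inconsistent that the plan uses ranks for association, which avoids relying on normality, yet makes no matching allowance in its descriptive rule.

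**Working it through.** The plan states no HBV-DNA mean, SD or median, so there is no figure to reproduce. The check has two parts: how poor a raw-scale summary could be, and whether anything in the plan depends on it.

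**Inputs.** From the documents: floor 2,000 IU/ml, that is log10(2,000) = 3.30; no ceiling. Assumed: the shape, location, spread and ceiling of the distribution.

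**1. Break-even for an uncut log-normal.** With log10 SD s and t = s·ln 10:
- mean/median = exp(t²/2)
- SD/mean = √(exp(t²) − 1)

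SD exceeds the mean when exp(t²) > 2, so when s > √(ln 2)/ln 10 = 0.8326/2.3026 = 0.36.

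**2. Truncated grid.** Log10 HBV-DNA normal with location 4.0 to 7.5 in steps of 0.5, SD 1, 1.25, 1.5 or 2, cut at 2,000 and at 1.7×10⁸ or 10⁹ IU/ml: 8 × 4 × 2 = 64 scenarios, by numerical integration.

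| Quantity | Ceiling 1.7×10⁸ | Ceiling 10⁹ |
|---|---|---|
| Mean/median | 2.11 to 52.7 | 3.89 to 133.2 |
| SD/mean | 1.20 to 7.48 | 1.73 to 12.1 |
| Share of patients below the mean | 67% to 90% | 74% to 92% |

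The mildest case (location 7.5, SD 1, ceiling 1.7×10⁸) has mean 3.38×10⁷, SD 4.07×10⁷ and median 1.60×10⁷, so mean − SD = −6.9×10⁶. On the log10 scale, mean − SD runs from 3.68 to 6.48 over the grid, always above the floor of 3.30.

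**3. Another shape.** If values are log-uniform from 2,000 to U:
- mean = (U − 2,000)/ln(U/2,000)
- mean square = (U² − 2,000²)/(2·ln(U/2,000))

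For U = 10⁵, ln 50 = 3.912. The mean is 98,000/3.912 = 25,051, the SD is 25,496 and mean − SD = −445. For U = 10⁴ the mean is 4,971, the SD 2,262 and the median √(2,000 × 10⁴) = 4,472. Mean/median is then 1.11 and the raw summary is acceptable.

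**4. Limits of the result.** A negative mean − SD does not follow for every log10 SD of 1 or more.

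| Assumption | SD/mean | Mean/median |
|---|---|---|
| Location 8, SD 1, cut at 1.7×10⁸ | 0.99 | 1.58 |
| Location 8.5, SD 1, cut at 1.7×10⁸ | 0.83 | 1.30 |
| Location 9, SD 1, cut at 10⁹ | 0.91 | 1.43 |
| Location 8, SD 1 to 2, values above 1.7×10⁸ recorded at that value | 0.73 to 0.84 | 0.88 to 0.97 |

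Mean − SD is positive in each row, and the documents rule none of them out. With recording at the ceiling, the grid's own location 7.5 with ceiling 1.7×10⁸ falls to SD/mean 1.01 to 1.03.

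**5. ALT.** For an assumed log-normal with natural-log SD 0.4, 0.7 or 1.0, mean/median = exp(s²/2) = 1.08, 1.28 or 1.65. The skew is mild to moderate, and it is assumed.

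**6. What depends on the scale.** Spearman's rho uses ranks, and log10 preserves order, so rho and its p-value are identical on either scale. MASLD is defined from CAP, obesity, diabetes and metabolic risk factors. MASH adds LSM, with ALT or histology. None of these uses a mean viral load, and eligibility is decided patient by patient.

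**The case for a change.** The strongest argument for a change is that it costs almost nothing. One sentence naming log10 IU/ml, or median and interquartile range in IU/ml, would remove the doubt. Eligibility has no ceiling, so nothing in the plan confines patients to the narrow range where a raw mean ± SD is acceptable. A second distributional shape gives a negative mean − SD with a maximum of only 10⁵ IU/ml. An analyst who reads the rule literally and takes the unit from the entry criterion would produce a poor table row.

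Much of this stands. The text is silent on scale, strong skew is plausible, and a raw-scale summary would probably serve readers badly. What does not stand is the step from silence to error. The plan nowhere commits to raw IU/ml, and mean ± SD of log10 values fulfils its sentence literally. The sizes above describe assumed inputs, not this study's patients. Requiring median and interquartile range for ALT would rest on assumed skew alone, and nothing in the documents singles ALT out from LSM or the other continuous variables.

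**Conclusion.** No change to the plan is needed. The gap is real but small: the scale on which HBV-DNA is summarised is not stated. Raw IU/ml would probably give an uninformative row, with the mean 2.1 to 133 times the median over the grid tried. That range rests wholly on assumed locations (4.0 to 7.5), spreads (log10 SD 1.0 to 2.0) and ceilings (1.7×10⁸ or 10⁹ IU/ml), and the negative mean − SD disappears under other assumptions that are equally open.

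This is reporting detail that an analyst fills sensibly on seeing the data, within the rule as written. The effect is confined to a descriptive entry. Every correlation, p-value and MASLD or MASH classification is the same whichever scale is used, and no endpoint or decision in the plan rests on mean viral load.
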